Endpoints	The fracture union rate for the investigational group will be shown to be non-inferior to the fracture union rate of the control group using a 10% non-inferiority margin and a one-sided 2.5% alpha. The sample size has been established to provide 80% power to demonstrate non-inferiority if the fracture union rates in the patient population are greater than 95%, and approximately the same when treated with TFNA or PFNA-II.
	Secondary Endpoints:
	• Adverse events (type and frequency) for all adverse events will be compared for the investigational and control groups
	• 24-week revision rate where revision is defined as removal of any component for any reason.
	• 24-week reoperation rate is defined as secondary surgery at the fracture site(s) for any reason
	Clinical Outcomes
	■ SF-12
	Harris Hip Score

■ EQ-5D
Radiographs: incidence of complications such as loosening or cut-out that require reoperation or revision

TIME AND EVENT SCHEDULE

	Enrolln	nent	Follow-up			
	FU1: Pre-	FU2:	FU3:	FU4:	FU5:	FU6:
Event/Visit	Ор	Surgery	1 week	6 weeks	12 weeks	24 weeks
	-90 to 0		1 to 14			
	days from		days			
	day of		after	±2		
Required Timing	surgery	0	surgery	weeks	±2 weeks	±4 weeks
The signing of the informed						
consent form	Х					
Inclusion/Exclusion criteria	Х					
Demographic data and medical						
history enquiry	Х					
Concise patient self-rated health						
measurement scale (SF-12v2)	Х				Х	Х
EQ5D	Х				Х	Х
Harris Hip Score					Х	Х
Subject history	Х					
Urine pregnancy test ¹	Х					
Frontal and lateral X-ray of						
fracture sites	Х		Х	Х	Х	Х
Surgical reduction and						
intramedullary nail fixation		Х				
Surgeon's evaluation on product						
operability during operation		Х				
Wound healing assessment ²			Х			
Local physical examination	Х		Х	Х	Х	Х
Concomitant drugs ³	Х	Х	Х	Х	Х	Х
Adverse event		X4	Х	Х	Х	Х
Serious adverse event		X4	Х	Х	Х	Х
Blood chemistry	Х	X ⁵				

1. Urine pregnancy tests: women of childbearing age only.

2. Wound healing condition is assessed until wound healing.

3. Concomitant Drug Table should include only pain killers and anti-osteoporosis drugs.

4. Adverse events and serious adverse events should be recorded starting at the time of patient randomization.

5.Second Laboratory Test analyses performed during post-op recovery phase per site standard of care. The results closer to the time of surgery will be recorded.

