10.9. Sample Size Justification

The sample size calculation is determined based on the primary endpoint using PROC POWER in SAS software version 9.3. It assumes that the fracture union rate at 24 weeks after surgery in the TFNA group would be equivalent to that of the PFNA-II group, and a common fracture union rate is approximately 95% or greater based on the literature review (see Section 1. 3.1). With a non-inferiority margin of 0.10 and a power of 80%, this implies a sample size of 75 for the TFNA and of 75 for PFNA-II surgery groups, respectively. The sample size will be increased to 188 (94 per group) to accommodate potential 20% attrition (see Section 1.3).

The sample size applies to patients enrolled, randomized, and actually treated. Some patients who enroll in a study and are randomized may not be ultimately treated for various reasons. Patient enrollment and randomization will continue until the proposed sample size for treated patients is complete.

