10.10.5 Analysis of the primary endpoint

In accordance with ICH guidance E9(²)the primary endpoint analysis will be based on the Per-Protocol set of patients for a comparison of the fracture union rates at Week 24 between TFNA and PFNA-II. Only patients in this analysis set with a known outcome for the primary endpoint will be analyzed.

The null hypothesis (TFNA is inferior to PFNA-II) will be rejected, and TFNA will be considered non-inferior to PFNA-II if the exact 97.5% upper one-sided confidence bound for the difference in fracture union rates between PFNA-II and TFNA at 24 weeks is less than non-inferiority margin, 10.0%.

Two sub-components of the primary endpoint at 24 weeks (radiographic outcome, and no deformation or breakage) will be compared between the two treatment groups.

Radiographic outcome, i.e. front/lateral X-ray films, will be assessed by the independent radiographic reviewer to determine if there are vague or fracture gap or continuous callus passing across the fracture line. The radiographic outcome will be summarized and compared at each follow up visit between the two treatment groups using Fishers exact test.

Similarly, the independent radiographic reviewer will also determine whether deformation or breakage of the implant has occurred. This outcome will be summarized between the two treatment groups at each follow up visit, as well.

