6.6 Significant level and statistical analysis software

For the primary endpoint, statistical analysis will be performed at the one-sided 0.025 significance level (corresponding to the one-sided confidence limit of the 95% confidence interval). For other endpoints, all statistical analysis will be performed at the two-sided 0.05 significance level (except for special instructions). SAS[®] 9.4 statistical software will be used for statistical analysis.

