6.7 Site merging principle

This trial is to be conducted simultaneously in multiple clinical trial institutions, and the actual number of subjects successfully included in each site will vary. In order to avoid the influence of too few actual number of subjects successfully enrolled in the site on the stability and reliability of the primary endpoint analysis results, the sites with the actual number of subjects successfully enrolled less than 10 will be merged. According to previous experience and reference, site merging generally adopts the following two methods:

- Sort the sites with the number of subjects actually enrolled less than 10 according to the site number, and merge the sites directly until the number of subjects in the sites is ≥10 after merging;
- (2) Merge the sites according to the principle of geographical proximity, and the number of subjects in the sites should be ≥ 10 after merging;

The site merging principle adopted in the statistical analysis will be further determined by the sponsor, the investigator and the statistician through a blind review meeting.

7. Statistical Analysis Indicators and Statistical Analysis Methods

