7.3 Primary endpoint

The primary endpoint is the fracture union rate 24 weeks after surgery.

Fracture union success is a composite endpoint; in order for an individual subject's surgery implanted with TFNA or PFNA-II to be considered successful he/she must satisfy all of the following criteria:

- 1. No focal tenderness or lengthwise percussion pain, or abnormal movement
- 2. The frontal/lateral X-ray examination shows the vague or no fracture gap, or the continuous callus passing across the fracture line
- 3. No deformation or breakage is found in the investigational product

Calculation principle: Based on the postoperative 24-week follow-up of the fracture status and the X-ray examination results of the fracture site, the calculation principle is as follows:

- 1. It is determined as 'Yes' when the focal tenderness, lengthwise percussion pain and abnormal activity at the postoperative 24-week follow-up of the fracture are filled as 'NA', 'NA' and 'No', respectively;
- 2. It is determined as 'Yes' when the X-ray examination at the fracture site 24 weeks after surgery shows that the fracture line is 'vague' or 'disappeared'; or that the frontal/lateral X-ray examination shows the continuous callus passing across the fracture line is filled as 'Yes';
- ③. It is determined as 'Yes' when the X-ray examination at the fracture site 24 weeks after surgery shows that the implant is filled as 'good';

If (1), (2) and (3) are determined as 'Yes', then the successful fracture union 24 weeks after surgery is determined as 'Yes'; if one of them is missing, it is determined as missing, that is, 'loss to follow-up during the trial'; others are determined as 'No';

For the primary endpoint, the analysis bases on the actual data (except missing data). LOCF (Last Observation Carry Forward) was used as sensitivity analysis for the missing of primary efficacy endpoints. The below 2 analysis tests will be used for the above analysis, and estimates of the differences in efficacy between the groups and bilateral two-sided 95% confidence interval will be given:

(1) CMH chi-square test with adjusted central effects;

Calculation method for non – inferiority P value:

Se=(Rate difference 95% upper limit of confidence interval - Rate difference 95% low limit of confidence interval)/2/ probit (1-0.05/2);

Z=(Investigational group-control group of difference in fracture union rates- non-inferiority margin)/Se;

P value=1-probnorm(Z);

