(2) Continuous correction Newcombe-Wilson for non-adjusted central;

The result from test (1) will used for the primary analysis result, the result from test (2) will be used as sensitivity analysis result. If the lower limit of the bilateral two-sided 95% confidence interval on differences in efficacy between the study group and the control group (equal to the lower limit of unilateral 95% confidence interval) is greater than -10%, it can be considered that the investigational product is not inferior to the control product

If the actual study results show that other baseline variables (such as age and gender) are significantly different between the study group and the control group, it will be fully communicated to the investigator in the data analysis stage. Based on the results of univariate analysis for baseline variables and primary endpoint, previous literature references and the clinical expert experience, the indicators affecting the primary endpoint to cause imbalance between groups, i.e., confounding factors, will be further specified. These indicators will be considered into the generalized linear model for correction and included into the sensitivity analysis of the primary endpoint analysis.

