2. The likelihood ratio Chi-square test or Fisher's exact probability test is used to analyze the intergroup comparison of qualitative indicators;

			-	
Indicator	Study group	Control group	Statistics	P value
Successful fracture union 24 weeks at	ter surgery ^{#1}			
Number of subjects (N miss)	XXX (XXX)	XXX (XXX)	X.XXXX	X.XXXX
Yes	XXX (XX.X%)	XXX (XX.X%)		
No	XXX (XX.X%)	XXX (XX.X%)		
Difference in success rate (study group - c	ontrol group) and 95% CI	XX.X% [XX.X	%; XX.X%]	
P value in non-inferiori	e 1/	X.XXXX		
Difference in success rate (study group - c	ontrol group) and 95% CI	XX.X% [XX.X	%; XX.X%]	
P value in non-inferiori	ty test #4	X.XXXX		
Successful fracture union 24 weeks at	ter surgery ^{#2}			
Number of subjects (N miss)	XXX (XXX)	XXX (XXX)		
Yes	XXX (XX.X%)	XXX		
		(XX.X%)		
No	XXX (XX.X%)	XXX		
		(XX.X%)		
Difference in success rate (study group - c	ontrol group) and 95% CI	XX.X% [XX.X	%; XX.X%]	
P value in non-inferiori	ty test #3	X.XXXX		
Difference in success rate (study group - c	• •	XX.X% [XX.X	%; XX.X%]	
P value in non-inferiori	ty test #4	X.XXXX		

Table 30 (FAS) Primary endpoint - Statistical analysis results of subjects'fracture union rate 24 weeks after surgery

Notes: 1. #3 is analyzed by CMH chi-square test with adjusted sites, estimate the difference in success rate and non-inferiority test the P value;

#4 is analyzed by Continuous correction Newcombe-Wilson for non-adjusted central, estimate the difference in success rate and non-inferiority test the P value;

2. #1: The primary efficacy indicators of the subjects lost to follow-up during the trial were not processed;

#2: The primary efficacy indicators of the subjects lost to follow-up during the trial were carried forward by LOCF;

3. If the lower limit of 95% CI of the difference in the rates of the study group and the control group is greater than the non-inferiority margin of -10%, then the investigational product is considered non-inferior to the control product, i.e., the non-inferiority conclusion is established in this trial.

Indicator	Study group	Control group	Statistics	P value
Site 01 Beijing Jishuitan Hospital - Su	accessful fracture unio	on 24 weeks after su	rgery	
Number of subjects (N miss)	XXX (XXX)	XXX (XXX)	X.XXXX	X.XXXX
Yes	XXX (XX.X%)	XXX (XX.X%)		
No	XXX (XX.X%)	XXX (XX.X%)		
Site 02 Peking University Third Hosp	ital - Successful fract	ure union 24 weeks	after surgery	
Number of subjects (N miss)	XXX (XXX)	XXX (XXX)	X.XXXX	X.XXXX

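### Protocol and SAP set different primary non-inferiority rules, and at 95% union with 75 per arm neither gives one-sided 2.5% alpha with 80% power

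*SAP*

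**What the plan says.** **Protocol.** Section 10.10.5 concludes non-inferiority if the "exact 97.5% upper one-sided confidence bound for the difference in fracture union rates", taken as PFNA-II minus TFNA, is below 10%. It does not say which exact bound.

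**SAP.** Section 7.3 lists two tests: a CMH test adjusted for site, and a continuity-corrected Newcombe-Wilson interval without adjustment. It then states "The result from test (1) will used for the primary analysis result" and makes the second a sensitivity analysis. The rule is that the lower two-sided 95% limit for TFNA minus PFNA-II exceeds -10%. The SAP gives no exact bound for the primary endpoint. Table 30, note 1, on analysis #3, adds only "3 is analyzed by CMH chi-square test with adjusted sites, estimate the difference in success rate and non-inferiority test the P value". Neither place gives an interval formula or variance. The p-value in 7.3 uses a standard error backed out of the interval width ("Rate difference 95% upper limit of confidence interval - Rate difference 95% low limit of confidence interval", divided by 2 and by the normal quantile).

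**Error rates.** SAP 6.6: "statistical analysis will be performed at the one-sided 0.025 significance level". The protocol synopsis sets the same alpha and says the sample size is meant "to provide 80% power to demonstrate non-inferiority if the fracture union rates in the patient population are greater than 95" per cent. Protocol 10.9 and SAP 6.2 share the sentence "With a non-inferiority margin of 0.10 and a power of 80%, this implies a sample size of 75 for the TFNA" (and 75 for PFNA-II), raised to 94 per arm for 20% attrition.

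**Strata.** SAP 6.7: "the sites with the actual number of subjects successfully enrolled less than 10 will be merged". The final number of strata is therefore not fixed in advance.

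**The concern.** These are two different pass/fail rules for the registration claim, and nothing says which governs or why the rule changed. At 95% union with 75 per arm only 75 × 0.05 = 3.75 failures per arm are expected. With so few events, exact, score and simple large-sample intervals differ materially in both alpha and power. If the SAP rule is more lenient than one-sided 2.5%, a pass under it may not stand under the protocol. If the exact rule governs, the trial has less power than stated.

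**Working it through.** **1. The plan's own figure.** Common rate 0.95, margin 0.10, one-sided 2.5%, power 80%, 1:1 allocation:

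n = 2 × 0.95 × 0.05 × (1.96 + 0.84)² / 0.10² = 74.6 (with unrounded quantiles), so 75 per arm. Attrition: 75 / 0.8 = 93.75, so 94.

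Both figures reproduce. The formula is an uncorrected normal approximation with unpooled variance.

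**2. Candidate rules at 75 per arm.** Alpha is taken at PFNA-II 95% / TFNA 85%, power at 95% / 95%. Unstratified and exact methods were enumerated over all outcomes, with exact p-values maximised over the unknown common rate. Stratified methods were simulated, mostly with 400,000 trials per setting.

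| Rule | Alpha | Power |
|---|---|---|
| Exact bound, score-ordered | 2.0% | 66.8% |
| Exact bound, ordered by raw difference | 0.03% | 4.5% |
| Symmetric Mantel-Haenszel, Sato variance, 10 sites | 3.6% | 81% |
| Symmetric Mantel-Haenszel, Greenland-Robins variance, 10 sites | 4.3% | about 82.5% |
| Site-stratified Miettinen-Nurminen, 10 sites | 2.1% | 66.8% |
| Newcombe, continuity-corrected (the SAP's test 2) | 1.5% | 61.5% |
| Newcombe, uncorrected | 2.6% | 71.8% |

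**3. Other union rates, 75 per arm.** Each cell is alpha / power.

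| Control union | Mantel-Haenszel (Sato, 10 sites) | Exact, score-ordered |
|---|---|---|
| 90% | 2.9% / 55% | 2.3% / 47.8% |
| 95% | 3.6% / 81% | 2.0% / 66.8% |
| 97% | 4.4% / 93% | 1.8% / 79.2% |
| 98% | 4.9% / 97% | 1.6% / 87.5% |
| 99% | 5.6% / 99.6% | 1.4% / 96.6% |

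Exact power reaches 80% only at a common rate of about 97.1%.

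**4. All 94 per arm evaluable, 95% union.** Mantel-Haenszel: alpha 3.3%, power 87.6%. Exact: power 78.3%. Stratified Miettinen-Nurminen: power 78.7% to 79.6% (10 to 5 sites).

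**5. How often the rules disagree at 95% / 95%.** Mantel-Haenszel passes and exact fails in 14.2% of trials with 10 sites and 14.8% with 5 sites at 75 per arm. At 94 per arm the figures are 9.3% and 9.6%. The reverse did not occur in 400,000 simulated trials.

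**6. One data set.** Failures are 5/75 on TFNA and 4/75 on PFNA-II, over ten sites with arms balanced within site and no site with failures in both arms.

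- Difference (TFNA minus PFNA-II union) = -1/75 = -1.33%.
- Sato variance = (0.0133 × 0.25 + 9/4) / 37.5² = 0.00160, so SE = 0.0400.
- Lower limit = -1.33% - 1.96 × 4.00% = -9.2%, above -10%: **pass**.
- Score-ordered exact p = 0.0276, above 0.025: **fail**.

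**The case against.** **The alpha excess is conditional.** The SAP gives no interval formula, and a standard error can be backed out of any interval's width. A Newcombe interval stratified with Mantel-Haenszel weights also fits the wording. It gives alpha of 2.2% to 2.4% and power of about 70%. This stands: the 3.6%, the disagreement rates and the -9.2% example all assume a symmetric Mantel-Haenszel interval. The standard-error formula points to symmetry but does not prove it. The alternative reading still misses 80% power.

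**The plan says 95% or more, and its literature reports union in all 389 PFNA-II subjects for whom it was given.** Higher rates do help exact power (87.5% at 98%). But the synopsis claims 80% for any rate above 95%, and at 97% exact power is 79.2%. Higher rates also worsen the Mantel-Haenszel alpha.

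**Attrition may be below 20%.** With no loss at all, exact power at 95% is 78.3%, under two points short. The 13-point gap needs both the lowest planning rate and full attrition, but those are the plan's own assumptions.

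**The one-sided 95% wording in SAP 7.3 is a slip.** Agreed: SAP 6.1 and 6.6 and the table notes make the intended limit clear, so no decision changes.

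**Conclusion.** The concern holds. The two documents state different primary decision rules, neither is fully specified, and neither, as evaluated, pairs one-sided 2.5% with 80% power at 95% union and 75 per arm. The exact bound holds alpha but has 66.8% power, about 13 points short. The CMH rule keeps about 81% power, but at alpha of about 3.6% if its interval is symmetric Mantel-Haenszel with Sato variance. Across variance formulas, 4 to 10 sites and within-site balance the range is 3.5% to 4.8% for alpha and 78% to 83% for power.

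The conflict and the exact figures are firm, given score ordering. The CMH figures rest on the symmetric-interval assumption. The 75 and 94 are correctly computed from their formula; the fault is that the formula matches neither analysis. This must be fixed, because the choice of rule can reverse the primary conclusion.

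**What to change.** 1. **Name one primary method that holds 2.5%, in both protocol 10.10.5 and SAP 7.3, before outcome data are compared by arm.** Two options are suitable:
   - a site-stratified Miettinen-Nurminen score interval, with sites merged per SAP 6.7, stratum weights stated, and the lower two-sided 95% limit for TFNA minus PFNA-II required to exceed -10%;
   - the protocol's exact bound, with score ordering stated.

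   Take the p-value from the same statistic as the interval.
2. **In SAP 7.3, describe the lower limit as one-sided 97.5%, not 95%.**
3. **Restate power in the protocol synopsis, protocol 10.9 and SAP 6.2 for the chosen method.** Across the two options it is about 67% to 69% at 95% union with 75 evaluable per arm, about 78% to 80% if all 94 are evaluable, and about 79% to 81% with 75 per arm at 97% union.

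**Cost.** Wording in both documents and a less favourable stated power; no extra patients if that power is accepted. Keeping 80% at 95% union takes about 96 evaluable per arm (exact 81.1%, stratified score 80.2% to 80.6%). At 20% attrition that is 96 / 0.8 = 120 per arm instead of 94, or 2 × 26 = 52 more patients.

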7.4 Secondary endpoints

Secondary endpoints include the safety and effectiveness results, imaging outcomes and adverse events.

(1) Adverse events (type and frequency) for all adverse events will be compared for the study and control groups

Calculation principle: Based on the collected adverse events in the CRF, if the subject has had at least one adverse event, it will be regarded as 'Yes'; otherwise, it will be 'No'.

The indicators in this part are mainly descriptive. Statistical analysis methods are the same as those in 7.1.

(2) 24-week revision rate, where revision is defined as any component removal for any reason.

Calculation principle: Based on the collected adverse events in the CRF, if the measure taken for the implant is filled as "Revision" and the difference between the date of occurrence of the event and the date of the operation is \leq 196 days, the revision is determined as "Yes"; if postoperative 24-week follow-up is failed, it is determined as "Missing"; others are determined as 'No';

The indicators in this part are mainly descriptive. Statistical analysis methods are the same as those in 7.1.

(3) 24-week re-operation rate, where re-operation is defined as secondary operation of the fracture site for any reason.

Calculation principle: According to the AEs in CRF. If AE "re-operation" site collected in the CRF and occurrence of the event and the date of the operation is \leq 196 days, it is determined as 'Yes'; if postoperative 24-week follow-up is failed, it is determined as 'Missing'; others are determined as 'No'.

The indicators in this part are mainly descriptive. Statistical analysis methods are the same as those in 7.1.

- (4) Clinical outcomes
- ➤ SF-12
- Harris Hip Score
- ► EQ-5D

Calculation principle for SF-12 Score:

SF-12 v2 Questionnaire (each item consists of 8 parts: body functions, physical conditions, body pain, general health, mental health, emotional conditions, social functions and vitality) and general physical and mental health assessment.

Calculation principle: SF-12 scores will be calculated by special software, and statistical analysis will be performed using "_NBS" variable.

The indicators in this part are mainly descriptive. The descriptive analysis results of the SF-12 score and the change from baseline at each follow-up will be given. The statistical analysis method is the same as 7.1. At the same time, the 95% confidence interval of the mean value of change value from each group, the

difference between groups and its 95% confidence interval are also provided.

Calculation principle for Harris hip score:

Total Harris hip score: It can be calculated by adding the scores of each sub-item.

(I) Regarding the complaint pain score (44 points in total), the specific points are as follows:

None, or ignores it (44 points)

Slight, occasional, no compromise in activities (40 points)

Mild pain, no effect on average activities (30 points)

Moderate pain, tolerable (20 points)

Marked pain, serious limitation of activities (10 points)

Totally disabled, crippled, pain in bed, bedridden (0 point)

(II) Function score (47 points in total): Gait score (33 points) + daily life score (14 points), the specific points are as follows:

Gait score (33):

- Support: None (11 points); Cane for long walks (7 points); Cane most of time (5 points); One crutch (3 points); Two canes (2 points); Two crutches or not able to walk (0 point)
- Distance Walked: Unlimited (11 points); Six blocks (30 minutes) (8 points); Two or three blocks (10 or 15 minutes) (5 points); Indoors only (2 points); Bed and chair only (0 point)
- ③ Limp: None (11 points); Slight (8 points); Moderate (5 points); Severe or unable to walk (0 point)

Daily life score (14 points):

- Put on Shoes and Socks: With ease (4 points); With difficulty (2 points); Unable (0 point)
- 2 Stairs: Normally without using a railing (4 points); Normally using a railing (2 points); In any manner (1 point); Unable to do stairs (0 point)
- ③ Enter public transportation: Yes (bus) (1 point); No (bus) (0 point)
- ④ Sitting: Comfortably in ordinary chair for one hour (5 points); On a high chair for 30 minutes (3 points); Unable to sit comfortably in any chair (0 point)

(III) Physical sign score (4 points in total), the specific points are as follows:

Whether all of the following conditions exist: (Less than 30° fixed flexion contracture; Less than 10° fixed internal rotation in extension; Less than 10° fixed

abduction; Limb length discrepancy less than 3.2 cm (1.5 inches);)

Yes (4 points), No (0 point)

- (IV) Physical examination score: Score result = The sum of A, B, C and D divided by 20; the specific points are as follows (refer to computation rule for Harris Hip Score in http://www.orthopaedicscores.com, which was approved by the Journal of Bone & Joint Surgery):

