5.2. Secondary Endpoints

The following secondary endpoints will be evaluated:

- Adverse events (type and frequency) for all adverse events will be compared for the investigational and control groups
- 24-week revision rate where revision is defined as removal of any component for any reason.
- 24-week reoperation rate is defined as secondary surgery at the fracture site(s) for any reason
- Clinical Outcomes
 - o SF-12
 - Harris Hip Score
 - o EQ-5D
- Radiographs: incidence of complications such as loosening or cut-out that require reoperation or revision

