8.4. Duration of Follow-up after Adverse Events

The Investigator should ensure that adequate medical care is provided to any subject for any adverse events, including clinically significant laboratory values, related to the study.

All adverse events related to the subject's participation in the study should be followed until the condition has resolved, or in the case of permanent impairment until the condition stabilizes and clinical outcome has been ascertained.

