7.7 Concomitant medication, adverse events (AEs) or serious adverse events

(SAEs)

For concomitant medication, the subject's concomitant medication is provided in the form of a list.

The AEs and investigational device-related AEs in subjects will be tabulated and summarized, respectively. The list of subjects reported with AEs/ investigational device-related AEs includes site number, random number, group, age, gender, name of AE (SOC code), name of AE (PT code), time of postoperative occurrence (day), remission time (day), severity, measures taken, outcome, correlation with surgery, correlation with investigational device, withdrawal from the trial due to AEs, whether it is unanticipated adverse device effect (UADE), device failure or SAE.

Investigational device-related AEs refer to those "definitely related", "probably related" and "possibly related" with the investigational device;

Time of postoperative occurrence (day) = Date of occurrence of AE - Date of surgery,

Remission time (day) = End date of AE - Date of occurrence of AE.

The summary form will list the total number of cases of AEs/investigational device-related AEs, the total number of subjects suffering from AEs/investigational device-related AEs.

Wherein, the total case of AEs refers to the number of subjects suffering from AEs, and the AEs occur in the subject at least one time, which is considered as "Yes";

Statistical analysis of the severity of adverse events, the relationship with the study device and the relationship with the surgery was performed. If multiple adverse events occurred in a patient, the analysis was performed with the most severe or highest correlation.

The SAEs and investigational device-related SAEs in subjects will be tabulated and summarized, respectively; such data will be presented in the same form as AEs. The list of subjects reported with SAEs/investigational device-related SAEs includes site number, random number, group, age, gender, name of SAE (SOC code), name of SAE (PT code), time of postoperative occurrence (day), remission time (day), severity, outcome, correlation with surgery, correlation with investigational device and SAE.

The list and summary of UADEs in subjects will be presented respectively in the same form as AEs.

The calculation method of the time of postoperative occurrence (day) and remission time (day), the presentation of the summary form and the statistical principle are the same as those for AEs.

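### SAP 7.4(2) dates a 24-week revision by the adverse event's occurrence, not by component removal, so a removal after day 196 for an earlier event would be counted

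*SAP*

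**What the plan says.** Protocol 5.2 names the endpoint as "24-week revision rate where revision is defined as removal of any component for any reason", and SAP 7.4(2) repeats it as "24-week revision rate, where revision is defined as any component removal for any reason". The thing to be counted is a procedure, and the time limit belongs to that procedure.

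The calculation principle in SAP 7.4(2) works from AE records and selects those whose implant measure is entered as *Revision*. The subject is a Yes when, for such a record, "the difference between the date of occurrence of the event and the date of the operation is" no more than 196 days. A failed 24-week follow-up is Missing, and everyone else is a No.

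SAP 7.7 shows what the occurrence date is. It defines "Time of postoperative occurrence (day) = Date of occurrence of AE - Date of surgery" and, separately, "Remission time (day) = End date of AE - Date of occurrence of AE". The AE listing (SAP Table 79) has columns for both intervals and for the measures taken, but none for the date of a procedure.

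For reoperation, SAP 7.4(3) reads "If AE 're-operation' site collected in the CRF and occurrence of the event and the date of the operation is" at most 196 days. The sentence is incomplete, and the AE it names is the reoperation itself.

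On follow-up, Protocol 8.4 says that AEs related to participation "should be followed until the condition has resolved", or until stable where impairment is permanent. Protocol 8.3 follows SAEs to resolution and lets the medical monitor ask for more information on events still open at study completion. Protocol 8.5 ends AE reporting when the subject's participation ends, and ends AE follow-up at resolution, stabilisation or study completion.

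**The concern.** In SAP 7.4(2), *Revision* is an attribute of an AE record and the date tested is that AE's date. A complaint and the operation that later treats it can be far apart. The rule asks whether an AE that led to revision started in time; the endpoint asks whether a component was removed in time. These differ when the AE starts by day 196 and the removal comes later.

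What is at stake is the meaning of each arm's rate. It is labelled a 24-week rate and is reported for a registration application, but it could include removals done after the window closed. It could also conflict with the primary endpoint data: a subject whose implant is in place and rated good on the 24-week X-ray could be tabulated as revised by 24 weeks.

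**Working it through.** **Inputs**
- Limit: 196 days from index surgery (SAP 7.4(2)). The 24-week window is days 140 to 196 (SAP 6.4).
- Planned size: 75 per arm, raised to 94 for 20% attrition (Protocol 10.9, SAP 6.2).
- Enrolment: about 8 to 10 months (Protocol synopsis).
- Revision counts: none in the documents.

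**1. The plan's own figures.** (24 + 4) × 7 = 196, the upper edge of the window. Nominal week 24 is 24 × 7 = 168 days. 75 / (1 − 0.20) = 93.75, rounded up to 94. All agree with the documents.

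**2. The rule applied to example pairs.** The day values are assumed, for illustration only.

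| AE onset (day) | Removal (day) | SAP rule: onset ≤ 196 | Removal ≤ 196 | Removal ≤ 168 |
|---|---|---|---|---|
| 100 | 120 | Yes | Yes | Yes |
| 150 | 180 | Yes | Yes | No |
| 160 | 200 | **Yes** | **No** | No |
| 190 | 230 | **Yes** | **No** | No |
| 200 | 210 | No | No | No |

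Only the third and fourth rows are changed by the choice of date. The second row is a Yes under either date and turns on the 196-day limit, so the issue concerns removals after day 196, not all removals after week 24.

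**3. Direction.** If onset is never later than the removal it leads to, then removal ≤ 196 implies onset ≤ 196. Every case counted by removal date is also counted by onset date, so onset dating can add cases and cannot lose any.

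**4. Size per case.** One added case moves an arm by 1/94 = 1.06 percentage points, or by 1/75 = 1.33 points if only 75 subjects contribute.

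**5. Time available.** Take the first subject's day 196 and the last subject's visit at day 168, with 30.4 days to a month. The gap is enrolment + 168 − 196 days:
- 8 months: 243 + 168 − 196 = 215 days, about 7 months.
- 10 months: 304 + 168 − 196 = 276 days, about 9 months.

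This is the longest case, for the first subject enrolled. It shrinks to nothing for the last, apart from the interval to lock, which the documents do not state. It shows that a late removal could reach the database, not that one would.

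**The case against.** **The event might mean the revision.** SAP 7.4(2) says event where SAP 7.7 says AE, so a reader could take the date to be that of the revision. This is possible but less likely: the sentence starts from AE records, and the SAP provides no other date. If it is what was meant, the text still needs to say so.

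**Late removals are not routinely captured.** This largely stands. Scheduled follow-up ends at 24 weeks and AE reporting ends with participation. What remains is a narrow route: an AE or SAE still open at exit, followed further under Protocol 8.3 or 8.4, then revised, with the record updated before lock. The effect is therefore probably small, but the rule remains wrong for the cases it reaches.

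**The endpoint is secondary and mainly descriptive.** True, and this limits the consequence. Allocation is 1:1 in blocks within site (Protocol 4.0), so time to lock should be balanced and no systematic difference between arms is expected.

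Three stronger readings are tempting, and the documents do not support them:
- *That the reoperation rule is shown to be wrong as well.* SAP 7.4(3) names an AE called re-operation. If that record is the second operation, its occurrence date is the operation date. The text is too garbled to settle this, so clarification is all that can be asked.
- *That the rate has no fixed time horizon.* AE onset is bounded at day 196. Only the removal date is left untested.
- *That sites opening at different times cannot be compared.* No by-site revision analysis is planned. By-site tables exist for union (SAP Tables 29 and 31), and the revision tables (35 and 45) are pooled.

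**Conclusion.** The point holds for the revision rate. As written, SAP 7.4(2) does not compute its stated endpoint: it tests when the AE occurred, not when a component came out. A removal after day 196 for an AE that began on or before day 196 would count if it were recorded before lock.

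The error can only raise a rate, by 1.06 points per case with 94 in an arm. How many cases there would be cannot be estimated from the documents; the follow-up rules suggest few. No between-arm bias is expected.

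This rests on three assumptions: the date of occurrence means AE onset, as SAP 7.7 indicates; onset never follows the removal it leads to; and some open events are followed past day 196. It is a small defect in a named secondary endpoint, worth correcting because the correction is nearly free.

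**What to change.** - In SAP 7.4(2), count a revision when the date of component removal minus the date of index surgery is at most 196 days. Take the removal date from the operation record, or by query where the CRF does not hold it. Protocol 11.3.1 already requires source documents to hold AE treatment and follow-up.
- List removals after day 196 separately, so that they are reported but not labelled as 24-week events.
- Reword SAP 7.4(3) so that the date tested is explicitly that of the second operation.

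The cost is a sentence in each rule, one listing and a few data queries. No other analysis changes.
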